EXPLORATORY HYPOTHESIS 3: Baseline imaging measures will differ in converters to BD diagnosis vs. non-converters as between BDD and UD in Hypothesis 1. Peak change and slope of change in scores for YMRS and, MSC-SADS will correlate negatively with baseline LOFC-amygdala resting state connectivity and posterior insula activation on the face emotion recognition task and positively with vACC-amygdala connectivity and dACC activation on the happy emotion NoGo-Go task.

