administered the following scales: The Mini International Neuropsychiatric Interview (M.I.N.I.) and the Family Interview for Genetic Studies (FIGS), the Structured Clinical Interview for DSM-IV-TR Axis II Personality Disorders (SCID II), Columbia Suicide Severity Rating Scale (CSSRS), Beck Scale for Suicide Ideation (BSSI), the Hamilton Depression Rating Scale 17-Item (HAMD) or the Children's Depression Rating Scale (CDRS-R), the Montgomery-Asberg Depression Scale (MADRS), the Hamilton Anxiety Rating Scale (HAMA) or the Screen for Child Anxiety Related Disorders (SCARED), the Young Mania Rating Scale (YMRS), the Childhood Events and Life Events Scales, the Hypomania Syndrome checklist of schedule for Affective Disorders and Schizophrenia (HSC-SADS), and the Clinical Global Impression Scale-for Bipolar Disorder (CGI-BP). Patients will then undergo a full physical examination (including heart rate, blood pressure, height and weight) and laboratory tests that will include complete blood count, comprehensive metabolic panel, thyroid function tests, electrocardiogram (EKG) urine examination and a urine toxicology screen. S100B and genetic blood draw will be completed at this time as well. There will also be a serum pregnancy test conducted at this visit. Full medication, medical, and psychiatric histories will be taken.

Visit 2 will consist of the mood questionnaires, Columbia Suicide Severity Rating Scale (CSSRS), Beck Scale for Suicide Ideation (BSSI), Visual Analog Mood Rating Scale (VAS), recording of vital signs and weight, and the baseline fMRI scan. The visit will last approximately 4 hours with approximately 2 hours being spent in the scanner itself. There are occasional circumstances that are beyond our control in which the subject will not be able to scan on the indicated week. If this occurs we will make every effort possible to scan the subject as soon as possible. Upon completion of the scan, UD patients, if they agree, will be started on antidepressant treatment. Patients will be educated in detail about the side effects of antidepressant treatment, ways to avoid side effects, and how to contact the research team in case of uncomfortable side effects. The study doctor will adjust the antidepressant dose as needed throughout the study. Genetic blood draw will also be done during this visit.

Only UD subjects who opt for treatment (and sign the appropriate consent) will complete the following visits:

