ii. Screening Items list for Manic Syndrome From the Schedule for Affective Disorders and Schizophrenia (MSC-SADS)³: consists of five items that can be rated on a scale of 1- 6 with a possible score of 5 – 30. SADS a precursor of DSM diagnostic criteria has been shown to have high reliability and validity³. Pertinent to current proposal, the MSC-SADS uses a score rather than a dichotomous measure of presence of absence of (hypo)mania. We decided to include the MSC-SADS in addition to the YMRS because this screening questionnaire has been very recently reported to be able to screen for bipolarity in patients with unipolar depression and predict the development of (hypo)mania¹. [name] the primary author of the study has agreed to be a consultant for this proposal.

- iii. **Clinical Global Impressions of Severity Scale-Bipolar Version (CGI-BP)**⁷⁸. The CGI-BP is a modified version of the original CGI designed specifically for use in assessing global illness severity and/or change in patients with bipolar disorder and assesses overall bipolar illness, depression, and mania.
- iv. **17-item Hamilton Depression Scale**⁷⁹ and **Hamilton Anxiety Scales**⁸⁰: are gold standards for assessing symptom severity of depression and anxiety respectively.
- v. **Life events scale**⁸¹ and **childhood events scales** would be used to document events which could contribute to development of depression. Scores would be used as covariates in the analysis.
- vi. **Treatment Emergent Side Effect Scale (TESES)**
- vii. **Columbia Suicide Severity Rating Scale (CSSRS)** Scale used for identifying the presence and severity of suicide ideation.
- viii. **Beck Scale for Suicide Ideation (BSSI)** Scale used for identifying the presence and severity of suicide ideation.
- ix. **Structured Clinical Interview for DSM-IV Personality Disorders (SCID-II)** Scale used for identifying the presences of DSM-IV personality disorders.
- x. **Montgomery-Asberg Depression Rating (MADRS)** Scale used by clinicians to assess the severity of depression among patients who have a diagnosis of depression.
- xi. **Screen for Child Anxiety Related Disorders (SCARED)** Scale used by clinicians to assess the severity of anxiety in pediatric patients.
- xii. **Children’s Depression Rating Scale, Revised (CDRS-R)** Scale used for rating the severity of depression in pediatric patients

Table 3. Baseline procedures for all subjects and Follow-up procedures for UD subjects

[figure not shown]

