where $h(t)$ is the hazard or rate of conversion at time (t), $h_0(t)$ is the baseline conversion rate and X_i for $i = 1, 2, \dots, p$ are covariates. The subjects will be followed in the fashion described in Table 3 with periodic assessments. The assumption of constant relative hazard rate over time will be tested and remedied if required following data transformation or by incorporating a piecewise constant hazard model. Based on this framework, we will test the significance of imaging and activation measures on the hazard rate. Our primary objective here is to identify those covariates that significantly affecting the hazard rate. The grouping of the UD (HRUD and LRUD) will be also treated as a separate covariate and put in the model as an indicator variable. To detect the progression of disease severity (episodes of (sub) threshold hypo(mania)) we will additionally use Young Mania Rating Scale (YMRS) and the mania syndrome checklist from the Schedule for Depression and Schizophrenia (MSC-SADS) between study visits over during follow-up. We will test the group difference between LRUD and HRUD using mixed-effects linear regression analyses⁹⁷ with repeated measurements taken over two years. Each model will include a random intercept and slope and fixed effects group, and time, as well as the stratification covariates. A likelihood ratio test will examine the incremental contribution of the group effect over time.

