Adjusting for covariates: These include behavioral rating such as, attentional variables such as response time, and accuracy of response, and changes in physiological ratings; demographic variables such as age, gender, and ethnicity; scores on behavioral measures such as anxiety; treatment with concomitant medications such as atypical neuroleptics during the study; treatment history, substance abuse, and trauma history; and structural variables such as whole brain and ROI volumes. We will first identify the covariates with highly correlated with the outcome measures. Next, from this pool of highly correlated covariates to guard against multicollinearity and to conserve for degrees of freedom to ensure that we have sufficient power. To control for potential confounding effects from these covariates and not over-fit in any of our models, we will use the forward stepwise regression model building approach - so that only one covariate will be included at a time in the model - which allows us to screen out covariates that are not related to our outcome measures by using an elevated p-value ($p=0.1$) and reserve statistical power to a limited number of variables that are shown to be associated with outcome measures in our data⁹⁸.

2c(ii)lb. Sample size and power consideration: Preliminary data obtained from BDD and UD subjects were compared with healthy subjects to obtain estimates of sample size at significance level set at 0.05. Proc Power of SAS software is used to estimate the sample size.

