These variables were chosen keeping in mind the most frequently cited risk factors for development of bipolar disorder in previous longitudinal studies of major depression

At least one of the following:

1. Family history of bipolar disorder in at least one first degree relative
2. History of any sub-threshold hypomania symptoms
3. History of mood episode related psychotic symptoms

Additional Inclusion criteria for Low Risk UD (LRUD) patients beside the inclusion criteria for UD:

These variables were chosen to minimize any overlap between the HRUD and LRUD groups.

1. No family history of BD in a first or a second degree relative
2. No past history of any sub-threshold hypomania symptoms
3. No history of psychotic symptoms

Exclusion criteria for UD and BDD patients:

1. Meeting DSM-IV criteria for schizophrenia, schizophreniform disorder, schizoaffective disorder, mental retardation, pervasive developmental disorder.
2. History of receiving electroconvulsive therapy in the past 1 year
3. Use of neuroleptics, mood stabilizers or benzodiazepines in the past 2 weeks.
4. Use of antidepressants in the past 2 weeks.
5. If on fluoxetine in the past, then should not have been on this medication for 5 weeks.
6. Acutely suicidal or homicidal or requiring inpatient treatment.
7. Meeting DSM-IV criteria for other substance/alcohol dependence within the past 6 months or abuse in the past 3 months, excluding caffeine or nicotine. The criteria will be evaluated by interview and urinary toxicology screening. The use of caffeine or nicotine will be recorded.
8. Use of alcohol in the past 1 week before the MRI scan.
9. No serious acute or chronic medical or neurological illness, including previously known HIV positive status (due to possible CNS involvement) as assessed by history, physical examination and laboratory examination including EKG, CBC and blood chemistry.
10. Current pregnancy or breast feeding.
11. Metallic implants or other contraindication to MRI.

Inclusion criteria for healthy subjects: Healthy subjects matched for age, gender and ethnicity will be included

1. Ages 15 - 30 years (inclusive) and able to give voluntary informed consent (consent will be taken from both parents and child for children under the age of 18)

2. No current or past history of psychiatric illness or substance abuse or dependence.
3. No current or past history of psychiatric illness or substance abuse or dependence in a first degree relative.

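### The Aim 3 imaging analyses neither name nor force in the baseline hypomania scores, so they would not show whether imaging adds to symptoms already measurable at the scan

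*Combined protocol and SAP*

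**What the plan says.** **Collection.** The Visit 1 description in 2c(ii)E lists the YMRS and the HSC-SADS at screening. Table 3 marks both at screening, at the baseline (scan) visit and at every follow-up visit.

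**Stated predictive value.** Section 2c(ii)G justifies adding the MSC-SADS because it has been reported to be "able to screen for bipolarity in patients with unipolar depression and predict the development of (hypo)mania".

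**Cox model.** Under Specific Aim 3 in 2c(ii)la, "we will test the significance of imaging and activation measures on the hazard rate". The one covariate named specifically for this model is risk group: "The grouping of the UD (HRUD and LRUD) will be also treated as a separate covariate". In the same paragraph the YMRS and MSC-SADS serve only to track progression during follow-up.

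**General covariate list.** The paragraph on adjusting for covariates covers task performance, demographics, "scores on behavioral measures such as anxiety; treatment with concomitant medications such as atypical neuroleptics during the study", treatment, substance and trauma history, and brain volumes. Covariates enter by forward stepwise selection at p = 0.1. Section E1a adds duration of illness, number of episodes and substance history. Neither place names a baseline hypomania score.

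**Change scores.** Exploratory Hypothesis 3 states: "Peak change and slope of change in scores for YMRS and, MSC-SADS will correlate negatively with baseline LOFC-amygdala" connectivity, with similar statements for the other imaging measures. No adjustment for the starting score is mentioned there.

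**The concern.** Section 2a(i) argues that clinical indicators are not enough and that further biomarkers are needed. For that purpose, the useful question in Aim 3 is whether a scan tells us more than a short checklist given at the same visit. The checklist is an early reading of the outcome, because the same scales later measure progression. If an imaging measure correlates with the current score, and the score predicts conversion, imaging will be associated with the hazard even when it carries no further information. A model without the score cannot separate the two cases. The results are meant to help plan larger definitive studies, so a measure that only restates the checklist could be carried forward.

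The risk-group indicator is an incomplete stand-in. HRUD status needs any one of three history items, of which "History of any sub-threshold hypomania symptoms" is only one. It is a yes/no record of the past, not the current score, so symptom differences within the HRUD group remain.

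The peak-change correlation raises a related problem. The baseline score is subtracted in forming the change, so any imaging-baseline link feeds into the result.

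**Working it through.** **Inputs from the documents.** 60 per UD group, 20% attrition, conversion 6% (LRUD) and 14% (HRUD), alpha 0.05, stated power 80% (2c(ii)lb, Specific Aim 3); YMRS below 10 at entry (E1a). The documents give no imaging-symptom correlation, no hazard ratio for the score and no score SDs; those below are assumptions.

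**1. The plan's own figure.** 60 × 0.8 = 48 per group, so expected conversions are 48 × 0.06 + 48 × 0.14 = 9.6. The group hazard ratio is ln(0.86)/ln(0.94) = 2.44. Two-sided power is 25.5% (two proportions) or 28.1% (Schoenfeld), so the stated 80% does not reproduce. The most favourable variant tried (annual rates, no attrition, one-sided) reaches 68.2%. The present point does not depend on this. What it uses is the event count: about 10.

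**2. Could stepwise selection miss a real predictor?** Approximate chance that a score enters at p < 0.1: Φ(ln HR × √D − 1.645), with D = 9.6 and √D = 3.098.
- HR 1.5 per SD: Φ(1.256 − 1.645) = 0.35, so missed about 65% of the time.
- HR 2 per SD: Φ(2.147 − 1.645) = 0.69, so missed about 31% of the time.

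**3. What happens if the score is left out?** Simulated Cox models: 48 per group, 6%/14% conversion, HRUD/LRUD indicator always in the model, HRUD mean score 0.5 SD higher (assumed), imaging with no effect given the score, likelihood-ratio test at 0.05, 2,000 runs per cell. Ranges are over score hazard ratios of 1.5 to 3 per SD.

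| Imaging-score correlation | Imaging significant, score omitted |
|---|---|
| 0.2 | 6.8-9.8% |
| 0.3 | 7.3-15.9% |
| 0.5 | 10.2-29.9% |

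With the score included, the rate over these cells is 5.4-6.3%. At zero correlation it is 4.6-5.6% with the score omitted and 5.1-7.2% with it included, so the ordinary likelihood-ratio test is itself slightly liberal with so few events.

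**4. What happens if the score is in the stepwise pool?** A run of 1,500 trials per cell (correlation 0.2-0.4, same hazard ratios) gave 4.7-5.9%. A repeat with 2,000 per cell and correlations 0.2-0.5 gave 4.8-7.3%, never more than 0.6 percentage points from the rate with the score forced in. The trials in which imaging would look falsely significant tend to be those in which the score is also selected. Step 2 therefore shows that the score will often be absent from the final model. It does not show that the error rate is inflated.

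**5. Peak change.** Let r_ib be the imaging-baseline correlation, r_bp the baseline-peak correlation and k = SD(baseline)/SD(peak). If imaging relates to peak only through baseline, then

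corr(imaging, peak − baseline) = r_ib (r_bp − k) / √(1 + k² − 2 r_bp k).

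With r_ib = 0.3:

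| k | r_bp = 0.3 | r_bp = 0.5 | r_bp = 0.7 |
|---|---|---|---|
| 1 | −0.18 | −0.15 | −0.12 |
| 0.5 | −0.06 | 0.00 | +0.08 |
| 0.3 | 0.00 | +0.07 | +0.15 |

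The sign turns on whether k exceeds r_bp. The entry limit on YMRS makes k well below 1 plausible.

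**6. Price of adjusting.** Detectable HR per SD at 80% power = exp[(1.960 + 0.842)/√(9.6(1 − R²))], where R² is the share of imaging variance explained by the other covariates: 2.47 at R² = 0, 2.58 at 0.09, 2.84 at 0.25.

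**The case against.** Four points deserve weight.

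**The list is open.** A reader might infer that the plan excludes the baseline scores. It does not. Anxiety is given only as an example of a behavioural score, and the selection procedure is meant for all the models. The YMRS and SADS scores could be put in the pool, and step 4 shows that this would bring the error rate close to nominal. What stands is that nothing commits the analyst to it.

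**Unadjusted prediction is a legitimate target.** A reader might infer that a significant unadjusted imaging term would be a false positive. If imaging tracks early symptoms that precede conversion, the marginal association is real. The concern is limited to added value over symptoms already known, and unadjusted results should be kept.

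**The change-score effect has no fixed direction.** A reader might infer that the coupling gives a correlation opposite in sign to the hazard result, or quote an error rate that assumes equal SDs. Step 5 supports neither, since the coupling can vanish or reverse. Moreover, Exploratory Hypothesis 3 is a hypothesis, not a model specification, so the absence of adjustment there is silence rather than a decision.

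**Instrument and setting.** The predictive claim is made for the MSC-SADS, whereas the Visit 1 description and Table 3 list the HSC-SADS. The documents do not say that these are the same. The claim also rests on a cited study not reproduced here, and the aim is labelled exploratory. These points lower the priority but do not remove the gap.

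**Conclusion.** The gap is real and modest. The plan collects a baseline score that it describes as predictive of the outcome, and it neither names nor forces that score into any Aim 3 imaging analysis. As written, the analysis need not show whether imaging adds to the checklist.

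The 7-30% against 5-6% contrast illustrates the mechanism. It applies only if the score is left out altogether, and it rests on the assumed correlations, hazard ratios and 0.5 SD group shift. For the peak-change correlation, the defensible statement is that baseline is mixed in, by about −0.18 to +0.15 under the assumptions shown. No direction or headline error rate should be claimed. This is a cheap improvement in an exploratory aim and does not invalidate the study.

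**What to change.** 1. In the Aim 3 Cox model, force in the scan-visit SADS hypomania score together with the HRUD/LRUD indicator, outside the stepwise procedure. Test one imaging measure at a time with a Firth penalised likelihood, given about 10 events.
2. For Exploratory Hypothesis 3, replace the correlation with peak change by a regression of peak score on the imaging measure plus the baseline score of the same scale. This removes the dependence on the SD ratio.
3. Report the unadjusted estimates beside both, labelled as answering the marginal prediction question.
4. State whether the MSC-SADS (Exploratory Aim 3, 2c(ii)G, 2c(ii)la) and the HSC-SADS (2c(ii)E, Table 3) are the same instrument, and use one name.

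**Cost.** SAP wording only, since the scheduled assessments already include the scores. The statistical price is one more parameter on about 10 events: the detectable hazard ratio per SD rises from about 2.47 to 2.58 or 2.84 if the score explains 9% or 25% of the imaging variance.

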Specific Aim 3: Using a conservative assessment of a 6% conversion rate for the LRUD group and 14% conversion rate for HRUD group, we calculate that with a sample size of 60 per group (HRUD and LRUD) we will have 80% power with type I error fixed at 0.05, under the assumption of 20% attrition rate in both groups, to detect statistically significant imaging measures as well as differential rate of conversion. We have used Bacsafra's⁹⁶ web based program to arrive at this power calculation. For sample size requirement to differentiate between HRUD and LRUD subjects via MSC-SAD and YMRS score peak-change and slope of change we will compare the mean baseline score and the mean peak scores using two sample t-test. Peak value for each group are extrapolated from usual values seen for YMRS iduring hypomania. Under the assumption of homogeneity among groups, for both the scales a sample of size 60 will be adequate even after adjusting for 20% attrition is adequate to ensure 90% power at alpha 0.05.

[figure not shown]

Fig. 8. Hypothetical YMRS peak score changes for HRUD and LRUD group over time

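### Stepwise covariate entry at p=0.1 in the Aim 3 Cox model, on about 10 to 18 expected converters, inflates false positives and hazard ratios

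*Combined protocol and SAP*

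**What the plan says.** Section 2c(ii)la, Specific Aim 3, models time to conversion with a Cox model in p covariates, where p is left open. It tests the imaging measures and gives the purpose as "Our primary objective here is to identify those covariates that significantly affecting the hazard rate". It adds that "The grouping of the UD (HRUD and LRUD) will be also treated as a separate covariate".

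The paragraph Adjusting for covariates, in the same section, names about 13 further variables (my count): response time, accuracy, physiological ratings, age, gender, ethnicity, anxiety, concomitant medication, treatment history, substance abuse, trauma history, whole-brain volume and ROI volumes. They are first screened for correlation with the outcome and then entered forward stepwise at p=0.1. The stated reason is "To control for potential confounding effects from these covariates and not over-fit in any of our models". The Cox model is not exempted.

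Section 2c(ii)lb, Specific Aim 3, assumes "6% conversion rate for the LRUD group and 14% conversion rate for HRUD group" without stating the period. With "a sample size of 60 per group (HRUD and LRUD) we will have 80% power with type I error fixed at 0.05", and "under the assumption of 20% attrition rate in both groups", it claims power "to detect statistically significant imaging measures as well as differential rate of conversion".

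For the Cox model the plan gives no expected number of converters, limit on terms, penalisation, multiplicity control or internal validation. Bonferroni adjustment and leave-one-out validation are written for Aim 1, and false discovery rate control for the activation analysis.

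**The concern.** Entering one covariate at a time limits the size of the final model, not the size of the search. When the best of about 13 candidates is picked repeatedly on about 10 events, the chosen terms fit chance features of the few risk sets that contribute. The remaining coefficients are then pushed away from zero, the tests become too liberal, and some fits do not converge.

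At stake is the use that Exploratory Aim 3 gives its results, the planning of larger definitive studies. A predictor that is noise, or a hazard ratio of 2.0 reported as 2.7, would misdirect or undersize such a study.

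**Working it through.** **The plan's own figure.** The stated power is 80%. For HRUD against LRUD with 48 per group (60 × 0.8), two-sided 0.05:

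- Two proportions: null SE = √(2 × 0.10 × 0.90 / 48) = 0.0612; alternative SE = √((0.06 × 0.94 + 0.14 × 0.86) / 48) = 0.0607; power = Φ((0.08 − 1.96 × 0.0612) / 0.0607) = 25%.
- Schoenfeld: HR = ln 0.86 / ln 0.94 = 2.44; power = Φ(0.891 × √9.6 / 2 − 1.96) = 28%.
- With annual rates, power is 44–56% two-sided, and at most 68% (one-sided, no attrition).

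The 80% is not reproduced. For a single continuous imaging measure alone in the model, 80% power at 9.6 events needs a hazard ratio of exp(2.80 / √9.6) = 2.47 per SD.

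**Expected converters.**

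- Rates over 24 months: 48 × 0.06 + 48 × 0.14 = 2.88 + 6.72 = 9.6 (12 with no attrition).
- Annual rates: 1 − 0.94² = 0.1164 and 1 − 0.86² = 0.2604, so 48 × 0.3768 = 18.1 (22.6 with no attrition).
- Chance of no LRUD converter, which makes the HRUD hazard ratio infinite: 0.94^48 = 5% on the first reading, 0.94^96 = 0.3% on the second.

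**Events per term.** Four imaging measures plus the risk-group indicator: 9.6 / 5 = 1.9. With 13 more candidates: 9.6 / 18 = 0.5. If all 13 are independent noise, the chance that at least one passes p=0.1 is 1 − 0.9^13 = 75%.

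**Simulation.** 48 per group; exponential conversion times matching the stated rates; independent covariates; all 13 candidates offered; likelihood-ratio tests at 0.05. The independence, the noise status of the 13 and the four forced measures are assumptions. Ranges span runs of different sizes, the largest being 598 null data sets and 400 with a true hazard ratio of 2.0 per SD for one measure.

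| Model | Events | False significance per measure | Any of four | Median HR (true 2.0) |
|---|---|---|---|---|
| Risk group + four measures, no search | about 10 | about 6% | about 20% | 2.1–2.2 |
| Same + stepwise from 13 | about 10 | about 14% | 33–43% | 2.5–2.7 |
| Same + stepwise from 5 | about 10 | 9% | – | 2.27 |
| Same + stepwise from 13 | about 18 | 8–9% | 25–29% | 2.3 |
| Risk group + one measure, ordinary Cox | about 10 | 5.3% | – | 1.99 |
| Risk group + one measure, Firth | about 10 | 5.4% | about 20% | 2.0 |

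The 14% is a central value: most runs gave 12–17%, and the smallest (150 data sets) 13–21%. With stepwise entry from 13 at about 10 events, 3–12% of fits diverged; at about 18 events none did in a run of 200. The last 20% is 1 − 0.946^4, for four separate models.

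The 95th percentile of the estimated hazard ratio, for a true 2.0, was 4.8–5.1 with five forced terms, 4.35 with one measure by ordinary Cox, and 3.7–3.9 with one measure by Firth.

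**The case against.** The strongest reply is that few events do little harm by themselves. At the same 10 events, the five forced terms give about 6% false significance per measure and a median of 2.1–2.2 for a true 2.0. A reader might infer from 9.6 converters that any Cox model here yields inflated hazard ratios and false predictors. The figures do not support that: the cost of few events alone is mainly wide intervals. The damage comes from the covariate search carried out on few events.

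Other points on that side:

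- **The count may be higher.** The period of the rates is unstated. At about 18 events the inflation shrinks by more than half but remains. The endpoint is also unsettled: section E2b6 counts subthreshold hypomania as an endpoint that ends participation, while section 2c(ii)F ties termination to the criteria for conversion. These passages must be reconciled, because the event count depends on them.
- **The plan does not clearly put four measures in this model.** In Exploratory Hypothesis 3 the four-measure sentence concerns correlations with symptom-score change. The converter sentence refers to Hypothesis 1, which names three (LOFC-amygdala, vACC-amygdala and dACC). Nor does the plan say that they enter together. This stands, so the any-of-four figures are illustrative.
- **The correlation screen may leave fewer candidates.** With five offered, the figures fall to 9% and 2.27. But a screen on correlation with the outcome is itself part of the search, so it does not restore the error rate.
- **Aim 3 is exploratory**, and the repeated YMRS and MSC-SADS analyses do not depend on the number of converters. This lowers the severity. It does not excuse a significance search for which 80% power is claimed.

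**Conclusion.** The concern holds for stepwise covariate entry in the Aim 3 Cox model. At about 10 events it roughly doubles the false-significance rate per imaging measure (about 6% to about 14%), raises it for any of four from about 20% to 33–43%, and moves the median estimate for a true hazard ratio of 2.0 to 2.5–2.7, with 3–12% of fits diverging. At about 18 events the figures are 8–9%, 25–29% and 2.3. The plan's assurance that the procedure avoids over-fitting therefore fails for this model.

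The size rests on independent noise covariates, on all 13 being offered, and on four forced measures. Fewer candidates or more events reduce it. The event count itself should be read as a range, not as a firm 9.6. As the aim is exploratory, this is a change that should be made, not a flaw that invalidates the study.

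**What to change.** - In Adjusting for covariates, state that stepwise selection does not apply to the Aim 3 Cox model.
- In Specific Aim 3, fit one pre-named imaging measure (per SD) at a time, with the HRUD indicator as the only other term. Name the measures of the converter hypothesis: LOFC-amygdala, vACC-amygdala and dACC. Include posterior insula only if the plan says so explicitly.
- Use Firth-penalised partial likelihood with profile-likelihood intervals. Dropping the search already brings the median back to about 2.0; Firth mainly handles the case of no LRUD converter and trims the upper tail.
- Replace the search for significant covariates by hazard ratios with intervals, labelled exploratory.
- In the sample-size section, state the period of the 6% and 14% rates and the resulting range of expected converters.

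The cost is wording and a standard software option; no more subjects or data are needed. There are real downsides. The imaging measures are not adjusted for one another, and this model has no adjustment for other confounders such as age or neuroleptic use. Separate tests at 0.05 still carry about a 14% chance of at least one false positive over three measures (1 − 0.95³), or about 20% over four at the simulated rate, unless adjusted.
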